6.3 Measures to minimize bias: randomization and blinding

Study participants will be randomized to the appropriate treatment (active or placebo) in their cohort using the Trial Supply Management system. The unblinded randomization list will be provided to pharmacies via a digital format. After informed consent is obtained, participants will be allocated a unique Screening number.

An interactive response technology (IRT) will be used for assigning eligible study participants to a treatment regimen (as applicable) based on a predetermined production randomization and/or packaging schedule provided by UCB (or designee). The IRT will generate individual assignments for kits of study medication, as appropriate, according to the visit schedule.

To enroll a study participant (Visit 0), the investigator or designee will contact the IRT and provide brief details about the study participant to be enrolled. Each study participant will receive a 5-digit number assigned at Screening that serves as the study participant identifier throughout the study. The study participant number will be required in all communication between the investigator or designee and the IRT regarding a particular study participant. Study participant numbers and kit numbers will be tracked via the IRT.

To randomize a study participant, the investigator or designee will contact the IRT and provide brief details about the study participant to be randomized. The IRT will automatically inform the investigator or designee of the study participant's randomization number. The IRT will allocate

kit numbers to the study participant based on the study participant number during the course of the study. The randomization number must be incorporated into the eCRF.

6.3.1 Procedures for maintaining and breaking the treatment blind

6.3.1.1 Maintenance of study treatment blind

All study participant treatment details will be allocated and maintained by IRT system.

The following individuals will receive the randomization code at the start of the study:

- Sponsor Patient Safety staff for reporting SAEs to regulatory authorities
- Designated bioanalytical staff analyzing PK samples
- IRT provider

■ The unblinded pharmacy monitors from the Contract Research Organization (CRO) and the Clinical Supply Set-Up Manager/Clinical Supply Planner, and the unblinded Clinical Project Manager (CPM)(or designee) will also have access to the treatment allocations and to the drug accountability records, if applicable. Further details are provided in the IMP Handling Manual and Site Unblinded Team Management Plan.

Due to differences in presentation between rozanolixizumab and placebo, special precautions will be taken to ensure blinding. Both products have packaging differences (unblinded labels) but also physical appearance differences (packaging presentation, volumes, color, viscosity). The IMP preparation will be performed by unblinded personnel. Please note that the difference in appearance of the two IMPs can be seen in the syringe but not in the tubing. Therefore, only the syringe will be covered by blinding stickers (see IMP Handling Manual).

The IMP administration will be performed by blinded qualified site staff.

The following individuals may, as necessary, request access to the randomization code from IRT as indicated:

- Interim analysis biostatistician/statistical programmer
- Members of the SMC who participate in unblinded sessions will be given information about the IMP allocation for those study participants for whom data are provided at these sessions (see also Section 9.7.2).
- The designated unblinded statistician and supporting programmer(s) responsible for the preparation of the data outputs for the SMC review and/or any interim analyses.

Certain clinical laboratory results have the potential to unblind the investigator, site personnel, and study team. These results will not be reported to investigative sites or other blinded personnel (see Section 10.2 for a list of these clinical laboratory parameters). A medical monitor independent from the study team and unblinded to the serum IgG and albumin levels, but blinded to actual treatment assignment (an independent unblinded medical monitor) will monitor these parameters during the Treatment Period. If temporary treatment discontinuation due to low serum IgG levels or low serum albumin levels (as per Section 7.1.4) is required, the independent

unblinded medical monitor will contact the IRT system to initiate mock infusions with only placebo. This procedure will take place irrespective of the randomized IMP. Allocation of mock kit numbers will be handled via the IRT. The independent unblinded medical monitor will re-initiate the IMP via the IRT system when the serum IgG and/or albumin levels have returned to protocol-defined thresholds specified in Section 7.1.4.

Further details of maintenance of the study treatment blind are provided in the IMP Handling Manual and Site Unblinded Team Management Plan.

6.3.1.2 Breaking the treatment blind in an emergency situation

In the event of an emergency, it will be possible to determine to which treatment arm the study participant has been allocated by contacting the IRT. All sites will be provided with details of how to contact the system for code breaking at the start of the study. The medical monitor or equivalent should be consulted prior to unblinding, whenever possible.

The CPM and medical monitor will be informed immediately via the IRT when a code is broken, but will remain blinded to specific treatment information. Any unblinding of the study medication performed by the investigator must be recorded in the source documents and on the Study Termination eCRF page.

Inadvertent unblinding must be listed as a major protocol deviation.

6.4 Treatment compliance

Drug accountability must be recorded on the Drug Accountability form (Section 6.2.1).

6.5 Concomitant medications/treatments

6.5.1 Permitted concomitant treatments (medications and therapies)

The following concomitant treatments are permitted during the study:

- Medications or therapies for FMS or chronic pain
 - PRN (as needed) analgesics taken as over the counter (OTC) (eg, ibuprofen, paracetamol, codeine) and/or prescribed (eg, opioids) if initiated [REDACTED] before randomization.
 - Prescribed regular opioids (short or long acting) up to a total opioid equivalent dose of 80mg/day of morphine (including PRN opioids, if taken). For regular opioids, the patient must have been on the stable equivalent daily dose of morphine for [REDACTED] after initiation/up-titration or [REDACTED] after down-titration.
 - Regular antidepressants or gabapentinoids (eg, pregabalin, gabapentin) prescribed for pain and/or sleep if started [REDACTED] and stable for [REDACTED] before randomization.
 - Migraine treatment-related drugs that are not antibody-based.
 - Any other pain therapies are only permitted if deemed acceptable in the judgment of the investigator and, where appropriate, in discussion with the medical monitor.
 - Any pain management programs are only permitted if deemed acceptable in the judgment of the investigator and in discussion with the medical monitor.

6.5.2 Prohibited concomitant treatments (medications and therapies)

Prohibited medications and therapies relative to Baseline are summarized in the table below. The use of these medications is also prohibited during the study and the use of these may result in the study participant being discontinued from IMP. Investigators should contact the medical monitor where possible to discuss the discontinuation of IMP in advance.

Concomitant medications prohibited during the study are presented in [Table 6-1](#).

Table 6-1: Concomitant medications prohibited during the study

Generic Name (commercial/trade name)	Exclusionary period relative to Visit 1 (regardless of route)
Immunosuppressive medications	
Cyclophosphamide (Cytoxan®)	6 months
Cyclosporine (Neoral®)	4 weeks
Biologics	
Monoclonal therapeutic antibodies	Used within 6 months of Visit 1 or used \geq 6 months prior to Visit 1 with B-cells that have not returned to normal levels
Others	
Antineoplastics or treatments for neoplastic disease (including anti-PD1 monoclonal antibodies)	3 months
Dabigatran	2 weeks
Intravenous methylprednisolone	4 weeks
Prednisone (or other steroids equivalent) ^a	4 weeks
Intravenous or subcutaneous immunoglobulin	6 weeks
Plasma exchange or plasmapheresis	6 weeks
Immunoabsorption	6 weeks

PD1 = programmed cell death protein 1

^a Except for a short course to treat, for example, an episode of asthma or chronic obstructive pulmonary disease exacerbation.

Table 6-2: Prohibited concomitant medications and therapies relative to the last rozanolixizumab dose

Generic Name (commercial/trade name)	Exclusionary period relative to Visit 1 (regardless of route)
Live vaccination	4 weeks
Treatment with IgG based monoclonal antibodies	8 weeks

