12. Study participant has a current or medical history of primary immunodeficiency.

13. Criterion removed.

14a. Study participants meet any of the following TB exclusion criteria:

- Known active TB disease
- History of active TB involving any organ system unless adequately treated according to World Health Organization/US Center for Disease Control therapeutic guidance and proven to be fully recovered upon consult with a TB specialist
- Latent tuberculosis infection (LTBI) (unless appropriate prophylaxis is initiated at least 1 week prior to IMP dosing and will be continued to completion of prophylaxis). Prophylaxis should be in accordance with applicable clinical guidelines and TB specialist judgment based on the origin of infection
- High risk of exposure to TB infection, as assessed by the investigator
- Criterion removed

For further information relating to definitions of known active TB, past history of TB, LTBI, and high risk of acquiring TB infection, see Appendix 12 (Section 10.12).

15. Criterion removed

16. Study participant has a history of solid organ transplant or hematopoietic stem cell/marrow transplant.

17. Study participant has a history of chronic ongoing infections (eg, Hepatitis B or C, human immune deficiency virus [HIV], or who tests positive for HIV, Hepatitis B or C at Screening Visit).

- Presence of Hepatitis B surface antigen at the Screening Visit.
- Positive Hepatitis C antibody test result at Screening or within 3 months prior to the IMP dose. NOTE: Study participant with a positive Hepatitis C antibody due to prior resolved disease can be enrolled only if a confirmatory negative Hepatitis C RNA test is obtained.

18. Study participant has undergone a splenectomy.

19. Study participant is pregnant or lactating.

20 Criterion removed.

21a. Study participant

- Has suicide attempt in the past 2 years (including an active attempt, interrupted attempt, or aborted attempt),
- OR had suicidal ideation with at least some intent to act in the past 6 months as indicated by a positive response (Yes) to either Question 4 or Question 5 of the Columbia Suicide Severity Rating Scale (C-SSRS) at Screening or Baseline (Visit 3);
- OR is otherwise judged clinically to be at a serious suicidal risk based on the investigator's judgment.

Prior/Concomitant therapy

22. Study participant has been treated with prohibited immunosuppressive medications, biologics, or other therapies within the exclusion period (see Section 6.5.2).

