23. Study participant has current treatment with prednisolone or equivalent (except for a short course to treat, for example, an episode of asthma or chronic obstructive pulmonary disease exacerbation).
24. Study participant has current treatment with morphine or equivalent of >80mg/day (>40mg/day if morphine or equivalent are taken in association with gabapentin [>1200mg/day] or pregabalin [>150mg/day]).
- 25a. Study participant has received a live vaccination within 4 weeks prior to Visit 1 or intends to have a live vaccination during the study or within 8 weeks following the final dose of IMP (Visit 28).

Prior/Concurrent clinical study experience

26. Study participant has previously been randomized in this study (rescreening for screen-failed participants is allowed with prior consultation and permission of the medical monitor/study physician; see Section 5.4).
27. Study participant has participated in another study of an IMP (and/or an investigational device) within the previous 30 days or 5 half-lives prior to screening (whichever is longer) or is currently participating in another study of an IMP (and/or an investigational device).

Diagnostic assessments

28. Study participant has alanine transaminase (ALT), aspartate aminotransferase (AST), or alkaline phosphatase (ALP) that is >2x upper limit of normal (ULN).
 - If study participant has >ULN for ALT, AST, or ALP that does not meet the exclusion limit at Screening, the tests must be repeated prior to dosing to ensure there was no further ongoing clinically relevant increase. In case of a clinically relevant increase as per the investigator's judgment, the study participant must be excluded.
 - Tests that result in ALT, AST, or ALP up to 25% above the exclusion limit (>2xULN) may be repeated once for confirmation. This includes rescreening. If any of the repeated tests (ALT, AST, or ALP) are >2xULN, the study participant will meet the exclusion criterion #28 and the study participant must be excluded.

- For randomized study participants with a Baseline result >ULN for ALT, AST, ALP, or total bilirubin but <1.5xULN, a Baseline diagnosis and/or the cause of any clinically meaningful elevation will have to be understood and recorded in the electronic case report form (eCRF).

29. Study participant has bilirubin >1.5xULN (isolated bilirubin >1.5xULN is acceptable if bilirubin is fractionated and direct bilirubin <35%).

30a. Study participant has IgG \leq 5.5g/L at the Screening Visit.

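### Table 6-2 counts its restrictions from the last rozanolixizumab dose in its title and from Visit 1 in its column header, and neither anchor fits both rows (minor)

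*Protocol*

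**What the plan says.** Protocol Section 6.5.2 has two tables under one lead-in: "Prohibited medications and therapies relative to Baseline are summarized in the table below". It adds that "The use of these medications is also prohibited during the study".

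- Table 6-1 lists treatments with exclusionary periods before Visit 1. For monoclonal therapeutic antibodies the entry begins "Used within 6 months of Visit 1", and it extends further back if B-cells have not recovered. Live vaccines are not listed.
- Table 6-2 is titled "Prohibited concomitant medications and therapies relative to the last rozanolixizumab dose". Its interval column carries the same header as Table 6-1: "Exclusionary period relative to Visit 1 (regardless of route". It has two rows: live vaccination, 4 weeks; IgG-based monoclonal antibodies, 8 weeks.

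The same subjects appear in Section 5.2. Criterion 25a excludes a participant who "has received a live vaccination within 4 weeks prior to Visit 1", or who "intends to have a live vaccination during the study or within 8 weeks following the final dose of IMP (Visit 28". Criterion 22 brings the Section 6.5.2 periods into eligibility: "Study participant has been treated with prohibited immunosuppressive medications, biologics, or other therapies within the exclusion period (see Section 6.5.2". Section 2.3 names 25a as the place where the live-vaccine restrictions are set.

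**The concern.** A title that looks back to the end of dosing and a header that looks back to the start of the study cannot both govern the same two numbers. Sites use this section after entry: Section 7.2.1 allows withdrawal for prohibited medication and refers to Section 6.5.2, not to 25a. Criterion 25a is an entry criterion about what the participant intends. It also labels the final dose as Visit 28, which a participant who stops early never reaches. Outside eligibility, Table 6-2 is the only place where a live-vaccine interval after dosing could be stated.

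The title's anchor is also hard to apply. Investigators are blinded in both Treatment Periods, so a site cannot routinely know the date of the last rozanolixizumab dose, and Sequence 3 has none.

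At stake is a live vaccine given sooner than the protocol's own 8 weeks to someone whose IgG the drug was meant to lower by about 70%. Randomization, endpoints and analysis are not touched.

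**Working it through.** **Step 1. Put each row under each anchor.**

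| Row of Table 6-2 | Counted from Visit 1 (header) | Counted from last rozanolixizumab dose (title) |
|---|---|---|
| Live vaccination, 4 weeks | Agrees with the pre-study limit in 25a (4 weeks) | Conflicts with the post-dose limit in 25a (8 weeks after final IMP) |
| IgG-based antibodies, 8 weeks | Conflicts with Table 6-1 (6 months, about 26 weeks; 26 − 8 = 18 weeks apart) | No conflicting text |

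Each reading leaves exactly one conflict, so choosing one label does not repair the table.

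**Step 2. Inputs for the calendar.** Nominal days from Table 1-2: Visit 26, the last possible active dose, is Day 162. Visit 28, the last IMP dose (placebo, in the Run-out), is Day 176. SFU/EOS is Day 218 ± 7 days. The Synopsis puts SFU/EOS 6 weeks after the last Run-out dose, and 176 + 42 = 218 reproduces the plan's figure. Section 7.2.1 sets the same 6 weeks from stopping IMP for early withdrawals.

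**Step 3. Completers, table read by its title.**
- Title rule ends: 162 + 28 = Day 190.
- 25a ends: 176 + 56 = Day 232, which is 232 − 190 = 42 days later.
- The during-study bar still covers the participant to SFU/EOS, leaving 232 − 218 = 14 days of 25a after the study.
- Day 218 is already 218 − 162 = 56 days (8 weeks) after the last possible active dose. With SFU/EOS at Day 211 this is 7 days short of 8 weeks; at Day 225 it is not short.

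For completers the practical effect is close to nil.

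**Step 4. Participants who stop on active drug, last dose at T, table read by its title.**
- Title rule ends at T+28; 25a ends at T+56. Difference: 28 days.
- If SFU/EOS is attended at T+42, the during-study bar runs until then and 56 − 42 = 14 days remain. With the ± 7-day window this is 56 − 49 = 7 to 56 − 35 = 21 days.
- If SFU/EOS is skipped (Section 7.2.1 only encourages completing the follow-up), the full 28 days are open.

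These figures measure the gap between two wordings. They do not measure risk.

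**The case against.** The best defence is that the intended meaning of the vaccine row can be worked out. The header, the lead-in and the first limb of 25a all point to the period before the study. The protocol's summary of changes, used here only as evidence of intent, describes the 4 weeks as time since a past live vaccination and says Table 6-2 was altered to match. Section 2.3 sends the reader to 25a. To do harm, a site would have to follow the title against all of these, for a participant who stopped on active drug and wants a live vaccine between weeks 4 and 8.

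Most of this stands, and it is why the point is minor. It does not clear the table. On the Visit 1 reading, the antibody row contradicts Table 6-1 in the same section and the title is wrong.

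Two stronger readings are tempting. A reader might infer that the protocol permits a live vaccine 4 weeks after dosing. The documents do not support that: it is the less likely reading of the row, and 25a states 8 weeks. A reader might also infer that a participant could enter 8 weeks after a monoclonal antibody. Criterion 22 with Table 6-1 keeps the 6 months.

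**Conclusion.** The contradiction is real and visible on the face of Table 6-2. It is a minor error in operative safety text, because the stricter rules exist in 25a and Table 6-1 and nothing in the analysis depends on it. The practical reach is confined to participants who stop while on rozanolixizumab, where the wordings differ by 28 days (T+28 against T+56), or by 14 days (7 to 21) beyond an attended SFU/EOS visit.

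The number affected cannot be estimated from the documents. A reader might build a count from the SAP's 25% drop-out with uniform timing. Assuming equal drop-out by sequence, 20 × 0.25 = 5 stop in each. Spread over 24 weeks, 5 × 24/24 + 5 × 12/24 = 7.5 of 60 would stop on active drug; spread over all 28 dosing weeks, 5 × 24/28 + 5 × 12/28 = 6.4. That is not an exposure estimate. It reuses a power assumption, it includes people who stop IMP but stay on study under the bar, and the documents say nothing about how many would seek a live vaccine.

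**What to change.** - Make Table 6-2 a post-treatment table, with title and header both counting from the final dose of IMP. 25a already uses this anchor, and a blinded site can apply it.
- Set live vaccination to 8 weeks to match 25a, and keep IgG-based antibodies at 8 weeks.
- Leave the limits before Visit 1 where they are: 4 weeks for live vaccines in 25a, 6 months for monoclonal antibodies in Table 6-1.
- In 25a, define the final dose as Visit 28 or the participant's own last IMP dose if earlier.

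The cost is a small wording change in the next amendment, with its ethics committee handling and a notice to sites. Visits, data collection and analysis are unchanged.

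There is one downside. Counting the antibody row from final IMP moves its end for completers from 162 + 56 = Day 218 to 176 + 56 = Day 232, 14 days past the nominal end of study, and applies it to participants who only ever received placebo. If the sponsor does not want that, it can keep the 8 weeks in that row as advice to Day 218 and correct only the vaccine row and the header.

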6.5.3 Rescue medication

The use of OTC analgesics (eg, ibuprofen, paracetamol, codeine) and other medications for treatment of FMS is allowable at a stable dose during the study (see Section 6.5.1). The use of these medications is considered rescue medication if the dose is increased relative to the stable dose or if an additional medication not used at Screening is considered necessary by the investigator. The date and time of rescue medication administration as well as the name and dosage regimen of the rescue medication must be recorded in the eCRF under concomitant medication (see Schedule of Activities, Section 1.3). As the rescue medication might overlap with the permitted medication, the rescue medication can be identified as a new analgesic not listed at screening or as a change in the usual dosage regimen of a permitted SoC analgesic medication.

6.6 Dose modification

Dose modification of IMP is not permitted in this study. However, temporary discontinuation of IMP may occur as detailed in Section 7.1.4.

6.7 Criteria for study hold or dosing stoppage

After approximatively 30 study participants have completed their 2 treatment periods, a planned interim analysis may be conducted (Section 9.7.1). A decision to halt the study may be taken based on this analysis, if performed.

The sponsor's decision for study hold may also be based on an SMC recommendation (see Section 9.7.2).

6.8 Treatment after the end of the study

There are no plans for the provision of rozanolixizumab after the end of the study. The study participant should discuss any alternative treatment options (if needed after the study) with their healthcare provider.

7 DISCONTINUATION OF STUDY MEDICATION AND PARTICIPANT DISCONTINUATION/WITHDRAWAL

[figure not shown]
7.1 Discontinuation of study medication

In addition to algorithmic stopping criteria, management of AEs is ultimately at the investigator's discretion.

7.1.1 Liver chemistry stopping criteria

Discontinuation of study treatment for abnormal liver function should be considered by the investigator when a study participant meets one of the conditions outlined in Figure 7-1 or if the investigator believes that it is in best interest of the study participant.

Figure 7-1: Liver Chemistry Stopping Criteria and Increased Monitoring Algorithm

AST=aspartate aminotransferase; ALT=alanine transaminase; INR=international normalized ratio; SAE=serious adverse event; ULN=upper limit of normal

Specific assessments and follow-up actions for potential drug-induced liver injury (PDILI) are provided in Appendix 6 (Section 10.6).

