7.1.2 Other permanent discontinuation criteria

Study participants **must permanently discontinue** IMP if any of the following events occur:

1. Study participant develops an illness that would interfere with their continued participation.
2. Study participant has a significant infective episode including but not limited to bacteremia/sepsis, infectious meningitis, septic arthritis, osteomyelitis, complicated pneumonia, or visceral abscess which may or may not result in hospitalization. This list is not intended to be all inclusive, and the investigator is expected to apply their clinical judgment on continuing IMP based on the clinical situation (see Appendix 14; Section 10.14).
3. Study participant has an AE of severe or serious hypersensitivity, infusion-related reaction (Appendix 15; Section 10.15), or anaphylaxis requiring corticosteroid and/or epinephrine therapy (Sampson et al, 2006).
4. Study participant has a recurrence of aseptic meningitis (see also Appendix 13; Section 10.13).

5. Participant meets PDILI permanent discontinuation criteria (see Appendix 6, Section 10.6).
6. Study participant for whom further examinations result in a diagnosis of active TB, or if the study participant is diagnosed with LTBI with no initiation of TB preventive therapy, prematurely discontinues TB preventive therapy, or, in the opinion of the investigator or sponsor is noncompliant with TB preventive therapy. An EW visit must be scheduled as soon as possible, but not later than the next regular visit.
7. Study participant has new onset or recurrent neoplastic disease (except for superficial basal or squamous cell carcinoma of the skin not requiring targeted biological therapy, chemotherapy, or radiation).
8. Study participant has active suicidal ideation as indicated by a positive response (Yes) to either Question 4 or Question 5 of the “Since Last Visit” version of the C-SSRS. The study participant should be referred immediately to a mental healthcare professional and must be withdrawn from the study.

7.1.3 Level of follow up to be considered when permanent discontinuation from IMP occurs

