10.6 Appendix 6: Liver safety – suggested actions and follow-up assessments

Study participants with PDILI must be assessed to determine if study medication must be discontinued. In addition, all concomitant medications and herbal supplements that are not medically necessary should also be discontinued.

Investigators should attempt to obtain information on study participants in the case of study medication discontinuation to complete the final evaluation.

Study participants with PDILI should not be withdrawn from the study until investigation and monitoring are complete. All results of these evaluations and observations, as well as the reason(s) for study medication discontinuation and/or study participant withdrawal (if applicable), must be recorded in the source documents. The eCRF must document the primary reason for discontinuation of study medication.

A specific monitoring plan must be agreed between the UCB study physician and the investigator for study participants who have ALT >3xULN. The monitoring plan should include any necessary follow-up assessments (until resolution of the abnormal laboratory values).

Phase 2 liver chemistry stopping criteria are designed to assure study participant safety and to evaluate liver event etiology. They are presented in the tables below.

Table 10-2: Phase 2 liver chemistry stopping criteria and follow-up assessments

Liver chemistry stopping criteria	
ALT-absolute	ALT \geq 5x ULN
ALT increase	ALT \geq 3xULN persists for \geq 4 weeks
Bilirubin^{a,b}	ALT \geq 3xULN and bilirubin \geq 2xULN ($>35\%$ direct bilirubin)
INR^b	ALT \geq 3xULN and INR >1.5 , if INR measured
Cannot monitor	ALT \geq 3xULN and cannot be monitored weekly for 4 weeks
Symptomatic^c	ALT \geq 3xULN associated with symptoms (new or worsening) believed to be related to liver injury or hypersensitivity
Suggested actions and follow-up assessments	
Actions	

Immediately discontinue study medication.Report the event to UCB within 24 hours.Complete the liver event CRF, and complete an SAE data collection tool if the event also met the criteria for an SAE.^bPerform liver chemistry follow-up assessments.	
Follow-up assessments	

Viral hepatitis serology^dObtain INR and recheck with each liver chemistry assessment until the transaminase values show downward trendObtain blood sample for PK analysis as soon as feasible after the most recent dose^e	

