Table 10-2: Phase 2 liver chemistry stopping criteria and follow-up assessments

Liver chemistry stopping criteria	

 Monitor the study participant until liver chemistry test abnormalities resolve, stabilize, or return to Baseline (see MONITORING). Do not restart/rechallenge study participant with study medication. Permanently discontinue study medication, and continue study participant in the study for any protocol-specified follow-up assessments Consider the need for a toxicology screening 
MONITORING:
 
If ALT $\geq 3 \times \text{ULN}$ AND bilirubin $\geq 2 \times \text{ULN}$ or INR > 1.5:
 
 Repeat liver chemistry tests (include ALT, AST, ALP, bilirubin) and perform liver event follow-up assessments within 24 hours. Monitor study participant twice weekly until liver chemistry test abnormalities resolve, stabilize, or return to Baseline. A specialist or hepatology consultation is recommended. 
If ALT $\geq 3 \times \text{ULN}$ AND bilirubin $< 2 \times \text{ULN}$ and INR ≤ 1.5:
 
 Repeat liver chemistry tests (include ALT, AST, ALP, bilirubin) and perform liver chemistry follow-up assessments within 24 to 72 hours. Monitor study participants weekly until liver chemistry abnormalities resolve, stabilize, or return to Baseline. 	
 Serum CPK and LDH Fractionate bilirubin, if total bilirubin $\geq 2 \times \text{ULN}$ Obtain complete blood count with differential to assess eosinophilia Record the appearance or worsening of clinical symptoms of liver injury (eg, fatigue, nausea, vomiting, right upper quadrant pain), or hypersensitivity, on the AE eCRF Record use of concomitant medications (including acetaminophen [or paracetamol], herbal remedies, and other over-the-counter medications) on the concomitant medications eCRF. Record alcohol use on the liver event alcohol intake eCRF Exclude pregnancy 
If ALT $\geq 3 \times \text{ULN}$ AND bilirubin $\geq 2 \times \text{ULN}$ or INR > 1.5:
 
 Anti-nuclear antibody, anti-smooth muscle antibody, Type 1 anti-liver kidney microsomal antibodies, and quantitative total IgG or gamma globulins. Serum acetaminophen adduct HPLC assay (quantifies potential acetaminophen contribution to liver injury in study participants with definite or likely acetaminophen use in the preceding week [James et al, 2009]). Liver imaging (ultrasound, magnetic resonance, or computerized tomography) and/or liver biopsy to evaluate liver disease; complete liver imaging and/or liver biopsy CRFs.

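### A met liver chemistry stopping criterion has a different force in protocol Sections 7.1.1 and 7.1.2 and Appendix 6, and the cross-references do not say which governs

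*Protocol*

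**What the plan says.** Five places in the protocol bear on a participant who meets a liver chemistry stopping criterion.

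- **Section 7.1.1** says "Discontinuation of study treatment for abnormal liver function should be considered by the investigator" when one of the conditions in the figure is met, or when the investigator thinks stopping is in the participant's interest. The figure is captioned "Figure 7-1: Liver Chemistry Stopping Criteria and Increased Monitoring Algorithm".
- **Section 7.1.2** lists events after which participants "must permanently discontinue" study drug. Item 5 is "Participant meets PDILI permanent discontinuation criteria", with a pointer to Appendix 6.
- **Appendix 6, Table 10-2** sets out six stopping criteria. Its actions include "Immediately discontinue study medication" and "Do not restart/rechallenge study participant with study medication", plus an instruction that the stop is permanent. The sub-heading over them, like the appendix title, describes the actions as suggested.
- **Appendix 6, Table 10-3** covers the increased-monitoring range, in which study drug may continue. A participant who then meets the stopping criteria is to be handled under Section 7.1.1.
- **Appendix 2**, in the footnote on clinical chemistry, says that Appendix 6 holds the stopping criteria and the required actions.

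**The concern.** A stopping rule should tell the investigator whether stopping is an obligation or a judgment. Here the same finding is met with a request to consider, an obligation, and firm instructions labelled both as suggestions and as requirements. At stake is whether a participant with a liver signal goes on being dosed, and whether that depends on which page the site reads.

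Oversight is affected as well. Protocol Section 9.5 and SAP Section 5.1.3 both have a category of important protocol deviation for withdrawal criteria. If the status of the rule is unclear, so is whether continued dosing after a met criterion counts as a deviation.

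**Working it through.** No arithmetic applies. The check is to set the passages side by side and follow the cross-references.

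**1. Who is affected.** Table 10-2 lists six criteria: ALT at least 5xULN; ALT at least 3xULN lasting at least 4 weeks; ALT at least 3xULN with raised bilirubin; ALT at least 3xULN with raised INR, if measured; ALT at least 3xULN that cannot be monitored weekly; and ALT at least 3xULN with relevant symptoms. The last two are not purely laboratory findings.

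**2. Force of each text for such a participant.**

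- Section 7.1.1: discretionary.
- Section 7.1.2, item 5: mandatory and permanent, provided that the list it refers to is Table 10-2.
- Table 10-2, wording of the actions: imperative, immediate and permanent.
- Table 10-2 sub-heading and Appendix 6 title: suggested.
- Appendix 2 footnote: required.

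**3. Where the cross-references lead.**

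- From Table 10-3 the site goes to Section 7.1.1, reads that stopping is to be considered, and is pointed on to Appendix 6 for follow-up actions. There Table 10-2 says to stop at once. The route runs from Appendix 6 to the softer text and back.
- From Section 7.1.2 the site goes to Appendix 6 and looks for permanent discontinuation criteria for potential drug-induced liver injury. No list has that name. Table 10-2 is the only one there that fits, but the reader has to infer it.

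**4. An example.** A participant is under Table 10-3 monitoring with ALT between 3 and 5xULN, and a repeat test reaches 5xULN. Table 10-3 directs the site to Section 7.1.1, under which an investigator may consider stopping and decide to continue. Section 7.1.2, read with Table 10-2, says the drug must be stopped for good. Both actions can be defended from the text.

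**5. Does a general rule settle it?** Section 7.1 leaves the management of adverse events to the investigator in addition to the algorithmic stopping criteria. That adds discretion to those criteria and does not replace them. It therefore does not explain why the section that introduces those criteria is itself worded as discretionary.

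**The case against.** The strongest reply is that the texts can all be obeyed together. An investigator who considers stopping under Section 7.1.1 and then follows Section 7.1.2 and Table 10-2 breaches nothing. The figure covers monitoring as well as stopping, so the soft verb may be a lead-in to a two-branch algorithm whose stop branch states its own action. The same sentence also covers stopping when no criterion is met, where discretionary wording is natural. The suggested label spans some items that really are optional. Sites are not left alone either: ALT above 3xULN needs a monitoring plan agreed with the sponsor's study physician, and stopping events go to the sponsor within 24 hours.

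Much of this is fair. The content of Figure 7-1 could not be read, so its conditions cannot be matched to Table 10-2. But the visible sentence applies to any condition in the figure without separating the branches, and Table 10-3 sends participants who meet stopping criteria to that sentence. The sponsor contacts limit divergence between sites; they do not state what the rule is.

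A reader might draw two stronger conclusions that the documents do not support.

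- **That the opening of Appendix 6 makes stopping optional.** It says "Study participants with PDILI must be assessed to determine if study medication must be discontinued". This can simply mean deciding whether Table 10-2 or Table 10-3 applies, which is compatible with mandatory stopping under Table 10-2. It is not itself a contradiction.
- **That the primary analysis is compromised.** Treatment discontinuation is the only intercurrent event listed in the primary estimand, and later data are excluded, so uneven application could change which data are analysed. But no event rate is given, about 60 participants are planned, and the adverse drug reactions listed in Section 2.3 include no hepatic event (SAP Section 5.6.5 does track hepatic disorders). An effect is possible and has not been shown.

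**Conclusion.** The inconsistency is real and should be corrected. For a met liver stopping criterion, Section 7.1.1 is softer than Section 7.1.2 item 5 and the Table 10-2 actions; the protocol calls the Appendix 6 actions both suggested and required; and the Table 10-3 cross-reference leads to the softest text. The ground is participant safety and consistent conduct across sites, not bias in the efficacy result.

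Its size is the number of participants who meet any of the six criteria, for which the documents give no figure; it may be small.

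Two assumptions carry the conclusion: that item 5 refers to Table 10-2, and that the stopping branch of Figure 7-1 covers the same criteria. The first rests on Table 10-2 being the only list that fits, the second on the figure's caption and the Table 10-3 cross-reference. If the figure states a firm action of its own, the sentence introducing it would still need to agree with it. This review takes no position on which status is clinically right.

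**What to change.** Reconcile the following so that each stopping criterion has one stated status, mandatory or discretionary, wherever it appears:

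- Section 7.1.1, together with Figure 7-1, separating stopping conditions from monitoring conditions;
- Section 7.1.2 item 5, which should name the list it refers to;
- the Appendix 2 footnote and the Table 10-2 heading, which should describe the actions in the same terms;
- the Table 10-3 cross-reference, which should lead to text with the agreed status.

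The sponsor's safety team decides which status applies. The cost is protocol wording and a notice to sites; sample size, endpoints and planned analyses do not change.
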